7.3 Guidelines for Evaluation of Measurable Disease

All measurements should be recorded in metric notation, using calipers if clinically assessed. All baseline evaluations should be performed as close as possible to the treatment start and never more than 4 weeks before the beginning of the treatment.

The same method of assessment and the same technique should be used to characterize each identified and reported lesion at baseline and during follow-up. Imaging based evaluation should always be done rather than clinical examination unless the lesion(s) being followed cannot be imaged but are assessable by clinical exam.

Clinical lesions: Clinical lesions will only be considered measurable when they are superficial and > 10 mm diameter as assessed using calipers (e.g. skin nodules). For the case of skin lesions, documentation by color photography including a ruler to estimate the size of the lesion is suggested. As noted above, when lesions can be evaluated by both clinical exam and imaging, imaging evaluation should be undertaken since it is more objective and may also be reviewed at the end of the study.

Chest X-ray: Chest CT is preferred over chest X-ray, particularly when progression is an important endpoint, since CT is more sensitive than X-ray, particularly in identifying new lesions. However, lesions on chest X-ray may be considered measurable if they are clearly defined and surrounded by aerated lung.

CT, MRI: CT is the best currently available and reproducible method to measure lesions selected for response assessment. This guideline has defined measurability of lesions on CT scan based on the assumption that CT slice thickness is 5mm or less. When CT scans have slice thickness greater than 5 mm, the minimum size for a measurable lesion

should be twice the slice thickness. MRI is also acceptable in certain situations (e.g. for body scans).

Ultrasound: Ultrasound is not useful in assessment of lesion size and should not be used as a method of measurement. Ultrasound examinations cannot be reproduced in their entirety for independent review at a later date and, because they are operator dependent, it cannot be guaranteed that the same technique and measurements will be taken from one assessment to the next. If new lesions are identified by ultrasound in the course of the study, confirmation by CT or MRI is advised. If there is concern about radiation exposure at CT, MRI may be used instead of CT in selected instances.

Endoscopy, laparoscopy: The utilization of these techniques for objective tumor evaluation is not advised. However, they can be useful to confirm complete pathological response when biopsies are obtained or to determine relapse in trials where recurrence following complete response or surgical resection is an endpoint.

Cytology, Histology: These techniques can be used to differentiate between PR and CR in rare cases if required by protocol (for example, residual lesions in tumor types such as germ cell tumors, where known residual benign tumors can remain). When effusions are known to be a potential adverse effect of treatment (e.g. with certain taxane compounds or angiogenesis inhibitors), the cytological confirmation of the neoplastic origin of any effusion that appears or worsens during treatment can be considered if the measurable tumor has met criteria for response or stable disease in order to differentiate between response (or stable disease) and progressive disease.

7.4 Response Criteria

7.4.1 Evaluation of Target Lesions

Prior to the first PD assessment, patients will be evaluated according the following RECISTv1.1 response:

Complete Response (CR): Disappearance of all target lesions, determined by two separate observations conducted not less than 4 weeks apart. There can be no appearance of new lesions.

Partial Response (PR): At least a 30% decrease in the sum of the longest diameter (LD) of target lesions, taking as reference the baseline sum LD. There can be no appearance of new lesions.

Progressive Disease (PD): At least a 20% increase in the sum of the LD of target lesions (with a minimum absolute increase of 5 mm), taking as reference the smallest sum LD recorded since the treatment started, or the appearance of one or more new lesions.

Stable Disease (SD): Neither sufficient shrinkage to qualify for PR (taking as reference the baseline sum LD) nor sufficient increase to qualify for PD (taking as reference the smallest sum LD since the treatment started).

For Cohort B only: After the first PD assessment per RECISTv1.1 (=irSD per irRECIST), patients will be evaluated for irPD at least 4 weeks apart according to the following definition:

Immune-related Progressive Disease (irPD): At least a 20% increase in the sum of the LD of target lesions (with a minimum absolute increase of

5 mm), taking as reference the smallest sum LD recorded since the treatment started, or appearance of new lesions since the last evaluation.

7.4.2 Evaluation of Non-Target Lesions

Complete Response (CR): Disappearance of all non-target lesions and normalization of tumor marker level. All lymph nodes should be non-pathological in size (<10 mm short axis).

Incomplete Response/Stable Disease (SD): Persistence of one or more non-target lesion(s) and/or maintenance of tumor marker level above the normal limits.

Progressive Disease (PD): Appearance of one or more new lesions and/or unequivocal progression of existing non-target lesions.

Although a clear progression on non-target lesions in absence of stable target lesions is exceptional, the opinion of the treating physician should prevail in such circumstances.

7.4.3 Evaluation of Best Overall Response

The best overall response is the best response recorded from the start of the treatment until disease progression/recurrence (taking as reference for progressive disease the smallest measurements recorded since the treatment started). The patient's best response assignment will depend on the achievement of both measurement and confirmation criteria.

Evaluation as per RECISTv1.1 and irRECIST.

Target Lesions	Non-Target Lesions	New Lesions	Overall Response per RECIST 1.1	Overall Response per irRECIST (Cohort B only)	Best Response for this Category Also Requires:
CR	CR	No	CR	N/A	>4 wks. confirmation
CR	CR Non-CR/SD	No	PR	N/A	>4 wks. confirmation
PR	CR Non-CR/PD	No			
SD	CR Non-CR/PD	No	SD	N/A	documented at least once >4 wks. from baseline
PD	Any	Any	PD	irSD	>4 wks. from baseline;
Any	PD*	Any			
Any	Any	Yes			
PD	Any	Any	N/A	irPD	No further confirmation required
Any	PD*	Any			
Any	Any	Yes			

*In exceptional circumstances, unequivocal progression in non-target lesions may be accepted as disease progression.

Note: Patients with a global deterioration of health status requiring discontinuation of treatment without objective evidence of disease progression at that time should be reported as "*symptomatic deterioration*." Every effort should be made to document the objective progression even after discontinuation of treatment.

N/A=not applicable

Note: If subjects respond to treatment and are able to have their disease resected, the patient's response will be assessed prior to the surgery

7.5 Duration of Response - Non prostate malignancies

Duration of overall response: The duration of overall response is measured from the time measurement criteria are met for CR or PR (whichever is first recorded) until the first date that recurrent or progressive disease is objectively documented (taking as reference for progressive disease the smallest measurements recorded since the treatment started).

The duration of overall CR is measured from the time measurement criteria are first met for CR until the first date that recurrent disease is objectively documented.

Duration of stable disease: Stable disease is measured from the start of the treatment until the criteria for progression are met, taking as reference the smallest measurements recorded since the treatment started.

7.6 Progression-Free Survival - Non prostate malignancies

Radiographic progression-free survival (PFS) is defined as the duration of time from start of treatment to time of radiographic progression as defined above in section 7.4 or death, the event that occurs first. Patients who have not experienced either event at the time of analysis will be censored at their last radiographic scan date.

Progression-free survival (PFS) is defined as the duration of time from start of treatment to time of radiographic or clinical progression or death, the event that occurs first. Patients who have not experienced either event at the time of analysis will be censored at the date of their last progression assessment.

7.7 Safety/Tolerability

Analyses will be performed for all patients having received at least one dose of study drug. The study will use the CTCAE version 4.03 for reporting of non-hematologic adverse events (<http://ctep.cancer.gov/reporting/ctc.html>).

8.0 ADVERSE EVENTS

8.1 Experimental Therapy

For the most recent safety update, please refer to the current Investigator's Brochure or Study Agent Prescribing Information.

Special Warnings and Precautions for Use

Subjects receiving nivolumab and/or ipilimumab are advised to use two acceptable (to treating investigator) methods of birth control (one of which must include a condom as a barrier method of contraception) starting at the time of informed consent and continuing

throughout the course of treatment and for at least 5 months (for women) and 7 months (for men) after nivolumab and/or ipilimumab immunotherapy is discontinued.

8.2 Adverse Event Reporting Requirements

Adverse event (AE) monitoring and reporting is a routine part of every clinical trial and is done to ensure the safety of subjects enrolled in the studies as well as those who will enroll in future studies using similar agents. Data on adverse events will be collected from the time of the initial study drug administration through 100 days after the last dose of study drug, that is nivolumab and/or ipilimumab. Any serious adverse event that occurs more than 100 days after the last study drug dose and is considered related to the study drug must also be reported. Serious Adverse Events (SAEs) will continue to be followed until:

- Resolution or the symptoms or signs that constitute the serious adverse event return to baseline;
- There is satisfactory explanation other than the study drug, nivolumab and/or ipilimumab, for the changes observed; or
- Death.

The investigator is responsible for the detection, documentation, grading and assignment of attribution of events meeting the criteria and definition of an AE or SAE. The definitions of AEs and SAEs are given below. It is the responsibility of the principal investigator to ensure that all staff involved in the trial is familiar with the content of this section.

Any medical condition or laboratory abnormality with an onset date before initial study treatment administration is considered to be pre-existing in nature. Any known pre-existing conditions that are ongoing at time of study entry should be considered medical history.

All events meeting the criteria and definition of an AE or SAE, as defined in Section 8.3, occurring from the initial study treatment administration through 100 days following the last dose of the study treatment must be recorded as an adverse event in the patient's source documents and on the CRF regardless of frequency, severity (grade) or assessed relationship to the study treatment.

In addition to new events, any increase in the frequency or severity (i.e., toxicity grade) of a pre-existing condition that occurs after the patient begins study treatment is also considered an adverse event.

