5.0 TREATMENT PLAN

5.1 Treatment Dosage and Administration

Protocol treatment must start within 14 business days of enrollment to the study.

- 5.1.1 In this study, Cohort A and Cohort B patients will start treatment with nivolumab dosed at 3 mg/kg IV and ipilimumab 1 mg/kg every 3 weeks for up to 4 doses. Cohort C patients will receive immunotherapy with nivolumab dosed at a flat dose of 480 mg IV every 4 weeks for up to 26 doses or 104 weeks.
- 5.1.2. Cohorts A and B maintenance immunotherapy with nivolumab dosed at a flat dose of 480 mg IV every 4 weeks will be continued for up to 23 doses or 92 weeks. Missed doses of 480 mg Nivolumab due to toxicity or general health condition will be skipped.

5.1.3 Total protocol therapy for all Cohorts will be up to 104 weeks during treatment. If disease progression or recurrence occurs during the follow-up phase, then per treating physician discretion, the patient may resume nivolumab 480 mg IV every 4 weeks until progression if tolerated with axial imaging as per protocol every, 12 weeks.

5.1.4 All study therapy will be administered on an outpatient basis.

Agent	Precautions	Dose	Route	Schedule	Cycle Length
Nivolumab (solution for injection) induction Cohort A and B only	Administer before other immunotherapy agents	3 mg/kg up to 4 doses	IV infusion over 30 minutes, +/- 10 minutes, with a sterile, nonpyrogenic, low protein binding 0.2 to 1.2 micrometer in-line filter. Follow with saline flush.	Day 1	3 weeks
Ipilimumab (solution for injection) induction Cohort A and B only	Administer 30 minutes after nivolumab.	1 mg/kg up to 4 doses	IV infusion over 90 minutes, +/- 10 minutes, through a non-pyrogenic, low protein-binding in-line filter. Separate IV line required.	Day 1	3 weeks
Nivolumab (solution for injection) maintenance After induction in Cohorts A and B; and throughout in Cohort C	Administer before other immunotherapy agents	480 mg up to 23 doses (92 weeks in Cohort A and B, and 104 weeks in Cohort C)	IV infusion over 30 minutes, +/- 10 minutes, with a sterile, nonpyrogenic, low protein binding 0.2 to 1.2 micrometer in-line filter. Follow with saline flush.	Day 1	4 weeks

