6.0 STUDY PROCEDURES

6.1 SCHEDULE OF ASSESSMENTS:

	Screening (within 28 days)	C1D1	C2D1	C3D1	C4D1	D1C5+	EOT¹²	Follow Up⁸
Informed Consent	X							
Review Eligibility Criteria	X							
Demographics, Height	X							
Prior and Concomitant Medications	X	X	X	X	X	X	X	
Review Adverse Events¹⁰	X	X	X	X	X	X	X	
Physical Examination, Vital Signs¹, Weight	X	X	X	X	X	X	X	
ECOG Performance Status	X	X	X	X	X	X	X	
Survival Status								X Q3m
Laboratory Assessments								
Pregnancy Test for WOBCP²	X							
CBC with diff, platelets³	X	X	X	X	X	X	X	
Comprehensive Metabolic Panel, including Alk Phos⁴	X	X	X	X	X	X	X	

	Screening (within 28 days)	C1D1	C2D1	C3D1	C4D1	D1C5+	EOT ¹²	Follow Up ⁸
LDH	X	X	X	X	X			
PSA¹¹	X	X	X	X	X	X	X	X
Testosterone¹¹	X				X		X	
TSH, free T3, free T4 (If Clinically Indicated: FSH, LH, ACTH)	X	X	X	X	X	X ⁶	X	
Therapy								
Cohorts A and B Nivolumab 3 mg/kg IV q3 wks for up to 4 doses¹³				X				
Cohorts A and B Ipilimumab 1 mg/kg IV q3 wks for up to 4 doses¹³				X				
Cohorts A and B Nivolumab 480 mg IV q4 wks for up to 23 doses¹³						X		
Cohort C Nivolumab 480 mg IV q4 wks¹⁴				X		X		
Imaging Tumor Assessments								
CT chest	X					X (q 12 wks)		
CT Abdomen/Pelvis or MRI Abdomen/Pelvis⁵	X					X (q 12 wks)		
Tc^{99m} Bone Scan (prostate only)	X					X (q 12 wks)		
QoL: BPI-SF and EORTC QLQ C30	X					X (q 12 wks)		
Correlatives								
Tumor Tissue Archival (CRPC preferred if available)	X							
Tumor Biopsy	X						X ⁷	
Research blood⁹		X	X	X		X (q 12 wks)	X	

1. Vital signs will include temperature, pulse, respirations, blood pressure; height will be obtained at screening only.
2. WOCBP: Women of child bearing potential; urine or serum pregnancy test.
3. CBC with diff includes total WBC, hemoglobin, hematocrit and differential of the WBC including absolute counts.
4. COMP or Comprehensive metabolic profile includes sodium, potassium, chloride, bicarbonate, BUN, creatinine, AST, ALT, alkaline phosphatase, total bilirubin.
5. With or without intravenous contrast, before or on associated visit. CT or MRI (preferred) brain with or without IV contrast if suspected or known brain metastases. Frequency of tumor assessments will be q12 weeks.
6. Every 42 calendar days ± 14 business days. May be delayed if infusion is not scheduled within the window.
7. Optional tissue biopsy collection at progression if subject consents; +/- 14 working days.
8. Follow up with phone call or with clinic visit.

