9. Blood for research should be collected prior to study treatment on C1D1, C2D1, C3D1 and C5D1, every 12 weeks thereafter and end of treatment.

10. Data on adverse events will be collected from the time of the initial study drug administration through 100 days after the last dose of study drug (nivolumab and/or ipilimumab) as described in Section 8.2.
11. For Cohort A only
12. End of Treatment Visit should occur within 3-4 weeks of last dose of protocol therapy.
13. Cohorts A and B (Nivolumab and Ipilimumab: 1 cycle (C) = 21 days (D) for up to 4 doses of Nivolumab (3mg/kg IV) and Ipilimumab (1mg/kg IV), then Nivolumab maintenance therapy alone (480mg IV): 1 cycle=4 weeks or 28 days (D). Total treatment time is up to 104 weeks.
14. Cohort C (Nivolumab monotherapy): 1 cycle (C) = 28 days (D) of Nivolumab monotherapy (480mg IV) for up to 104 weeks.

NOTE:

All procedures in study assessments schedule have a window of \pm 3 business days unless otherwise mentioned. Virtual clinic visits will be allowed per clinician/ subject discretion.

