8.3 Definitions

Adverse Event

An adverse event (AE) is any untoward medical occurrence in a patient receiving study treatment and which does not necessarily have a causal relationship with this treatment. An AE can be any unfavorable and unintended sign (including an abnormal laboratory finding), symptom, or disease temporally associated with the use of an experimental intervention, whether or not related to the intervention.

- *Diagnostic and therapeutic non-invasive and invasive (i.e., surgical) procedures will not be reported as adverse events. However, the medical condition for which the procedure was performed must be reported if it meets the definition of an adverse event unless it is a pre-existing (prior to protocol treatment) condition.*

- *Abnormal laboratory values or test results constitute adverse events if they induce clinical signs or symptoms or require therapy. They are to be captured under the signs, symptoms or diagnoses associated with them.*

Serious Adverse Event

An adverse event is considered “serious” if, in the view of either the investigator, it results in any of the following outcomes:

- Death
If death results from (progression of) the disease, the disease should be reported as event (SAE) itself.
- A life-threatening adverse event
An adverse even is considered ‘life-threatening’ if, in the view of either the investigator [or sponsor], its occurrence places the patient or subject at immediate risk of death. It does not include an adverse event that, had it occurred in a more severe form, might have caused death.
- Inpatient hospitalization or prolongation of existing hospitalization for ≥ 24 hours.
- A persistent or significant incapacity or substantial disruption of the ability to conduct normal life functions
- A congenital anomaly/birth defect
- Important medical event
Any event that may not result in death, be life-threatening, or require hospitalization may be considered serious when, based upon appropriate medical judgment, they may jeopardize the patient and may require medical or surgical intervention to prevent one of the outcomes listed in this definition of “Serious Adverse Event”. Examples of such medical events include allergic bronchospasm requiring intensive treatment in an emergency room or at home; convulsions that do not result in inpatient hospitalization or the development of drug dependency or drug abuse.

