10.0 CORRELATIVES/SPECIAL STUDIES

Specimens will be collected for banking and archival purposes. Submission of samples for correlative studies is expected of all subjects at baseline and optional tumor biopsy will be performed for those who consent to it.

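### Complications of the optional screening biopsy that begin before first dose are not collected as AEs or reported as SAEs, although the schedule places both the biopsy and an AE review at screening

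*Combined protocol and SAP*

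**What the plan says.** Section 6.1 (Schedule of Assessments) has a screening column with a mark for Tumor Biopsy and a mark in the row "Review Adverse Events¹⁰". The superscript leads to footnote 10, which states: "Data on adverse events will be collected from the time of the initial study drug administration". Section 8.2 repeats that start point.

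Section 8.2 then classifies what comes earlier: "Any medical condition or laboratory abnormality with an onset date before initial study treatment administration is considered to be pre-existing in nature". Pre-existing conditions still present at study entry go to medical history, and worsening after treatment begins counts as an AE. Section 8.3 defines an AE as "any untoward medical occurrence in a patient receiving study treatment". Section 8.5.2 starts SAE reporting to the drug supplier at first dose. Section 8.5.1, on reporting to the Coordinating Center, gives no start date and covers both SAEs and unanticipated problems.

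On the biopsy, Section 10.0 says "optional tumor biopsy will be performed for those who consent to it", and Section 10.1 lets a patient who declines a fresh biopsy enroll. In the schedule only the end-of-treatment biopsy carries a footnote to that effect (footnote 7): "Optional tissue biopsy collection at progression if subject consents". The screening cell has none.

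**The concern.** A fresh biopsy taken for the study's exploratory aims is an invasive procedure that can harm a patient before any drug is given. The plan schedules it, schedules an AE review in the same column, and then applies rules under which nothing found before first dose can be an AE. A patient admitted with bleeding after the biopsy, before cycle 1 day 1, would have a condition that Section 8.2 calls pre-existing, although the study caused it.

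What is at stake is safety oversight. The quarterly review in Section 12.0 looks at AE and SAE reporting, so an event that cannot become either may not reach the sponsor-investigator or the monitoring committee by that path. No section gives a separate rule for complications of screening procedures.

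**Working it through.** The plan gives no figure to reproduce, and no power or sample-size calculation is involved. The check sets the rules side by side and traces what happens to a biopsy complication.

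**Start of capture**
- Footnote 10 and Section 8.2: AE data from first dose.
- Section 8.3: an AE needs a patient on study treatment, and an SAE is an AE with a serious outcome. Section 8.5.1 has no start date, but its SAE limb therefore does not clearly reach a pre-dose event.
- Section 8.5.2: SAEs to the drug supplier from first dose.
- Section 8.4.2: attribution is to study treatment only; there is no procedure category.

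**Length of the uncovered interval**
- The screening column allows 28 days but does not say whether they are counted back from registration or from first dose.
- Section 5.1: "Protocol treatment must start within 14 business days of enrollment to the study". Ignoring holidays, 14 business days is two working weeks (14 calendar days) plus 4 business days (4 calendar days, or 6 if a weekend intervenes), so 18 to 20 calendar days.
- If the 28 days run to first dose, the interval is up to 28 days. If they run to registration, it is up to 28 + 20 = 48 days.

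**Fate of a screening-biopsy complication**

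| Course of the event | AE or SAE? | Other place it could appear |
|---|---|---|
| Starts and resolves before first dose | No | Source notes (Section 13.0); unanticipated problem if Section 8.7 is met |
| Still ongoing at study entry, no worsening | No | Medical history (Section 8.2) |
| Starts after enrollment, before first dose | No | Pre-existing under Section 8.2; whether it counts as ongoing at study entry is not defined |
| Worsens after first dose | The worsening is an AE | Original event as above |
| Patient never dosed | No | Outside the safety analysis (Section 7.7); screen failures appear on a log without a study number (Section 4.0), and enrolled undosed patients are replaced (Section 5.8) |
| Comparison: end-of-treatment biopsy, onset within 100 days of last dose | Yes | Not needed |

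The last row shows the asymmetry: a complication of the same procedure is an AE after treatment and not before it.

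**The unanticipated-problem route.** Section 8.7 requires all three of: unexpected, related to participation, and suggesting greater risk than already known. It has no first-dose start. Section 8.3 judges an AE's expectedness by the package insert, Investigator's Brochure, protocol and consent document. The protocol lists no biopsy complications and the consent text is not available here, so expectedness cannot be settled. The third criterion alone keeps the route narrow.

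**Number exposed.** Planned enrollment is 25 + 15 + 25 = 65. That is a ceiling for enrolled patients having a screening biopsy; consented patients who fail screening or are replaced would add to it. Because the biopsy is optional and no uptake is stated, the lower end is zero.

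**The case against.** The strongest reply is that a first-dose start is a deliberate and consistent choice. It appears in footnote 10 and Sections 8.2, 8.3 and 8.5.2, and it fits secondary endpoint 2.5.2 and the safety set in Section 7.7, both of which concern treated patients. The screening AE review also has its own purpose: criterion 3.1.8 requires recovery from earlier toxicities, and Section 8.2 needs a baseline against which to judge worsening. This stands. A reader might take the screening mark as a flat contradiction of its footnote; the documents do not support that, because a baseline review can be useful without generating reportable events.

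A reader might also infer that biopsy complications go wholly unrecorded and unreported. That is too strong. Source records, medical history and post-dose worsening each catch some, and the unanticipated-problem route is not shown to be closed.

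Nor does the schedule make the screening biopsy compulsory. Section 10.1 plainly allows enrollment without it, so the missing footnote is a minor inconsistency that could mislead a site reading only the table.

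What the reply does not answer is the classification rule. Consistency about drug-related capture does not explain why harm from a study procedure should be labeled pre-existing, and none of the other routes makes the original pre-dose event an AE or SAE.

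**Conclusion.** The point holds as a gap in safety capture. Under the current text, a complication of the optional screening biopsy with onset before first dose is neither collected as an AE nor reported as an SAE. The gap is complete, as far as AE and SAE routes go, for events that start and resolve before dosing and for patients never dosed. It is partial for events that persist or worsen.

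Its size in patients cannot be estimated from the documents. A reader might multiply an assumed serious-complication rate of 1% to 5% by 65 biopsies and get 0.65 to 3.25 events. That rests on a rate the documents do not contain and on every enrolled patient accepting an optional procedure, so it should not be presented as an expected count.

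The primary endpoint, sample size and efficacy analyses are unaffected, as is the description of drug safety in treated patients. The conclusion assumes that no separate manual or consent text, unseen here, already requires procedure-related events to be reported from consent.

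**What to change.** 1. In Section 8.2 and footnote 10, collect SAEs, and AEs related to any study-specific procedure (naming the optional screening biopsy), from signed consent; collect all other AEs from first dose as now. Referring to study-specific rather than required procedures keeps the optional biopsy inside the rule.
2. Restrict the pre-existing sentence in Section 8.2 to events not related to a study procedure and, for consistency with item 1, exempt SAEs with onset after consent.
3. Make matching changes to the AE definition in Section 8.3 and to the SAE start in Section 8.5, including 8.5.2. Without these, item 1 has no effect, because a pre-dose event would still not meet the AE definition. A procedure option in the Section 8.4.2 attribution scale would let sites record the cause.
4. State that the rule covers consented patients who are never dosed, and how a screen failure's event is identified when no study number has been assigned. List such events separately, so the treated safety set in Section 7.7 stays as defined.
5. Footnote the screening biopsy cell in Section 6.1 as optional, in line with Sections 10.0 and 10.1.

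The cost is a short amendment across these sections and a few extra pre-dose AE and SAE forms. The screening AE review already in the schedule provides the visit, and no efficacy analysis changes.
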